## STATISTICAL ANALYSIS PLAN

**Table 6 Adverse events within the first 42 days**

Adverse events	AL+Placebo	AL+AQ	ASMQ+Placebo	ASMQ + PPQ
Number of subjects	XXXX	XXXX	XXXX	XXXX
Vomiting/number of treatments, n/N, (%)	XXX/XXXX (XX.X)	XXX/XXXX (XX.X)	XXX/XXXX (XX.X)	XXX/XXXX (XX.X)
Serious adverse events (SAEs), n/N, (%)	XX/XXXX (XX.X)	XX/XXXX (XX.X)	XX/XXXX (XX.X)	XX/XXXX (XX.X)
Possible, probable or definite drug related SAEs, n/N, (%)	XX/XXXX (XX.X)	XX/XXXX (XX.X)	XX/XXXX (XX.X)	XX/XXXX (XX.X)
QTc >500ms (H4 and H48/H52)	XXX/XXXX (XX.X)	XXX/XXXX (XX.X)	XXX/XXXX (XX.X)	XXX/XXXX (XX.X)
Change from baseline in haemoglobin at days 3, 7, 28 (stratified for G6PD status)	XXX/XXXX (XX.X)	XXX/XXXX (XX.X)	XXX/XXXX (XX.X)	XXX/XXXX (XX.X)
Grading of adverse events, n/N, (%)	1-2	3-4	1-2	3-4
Symptoms, n/N (%)	X/XX (X.X)	X/XX (X.X)	X/XX (X.X)	X/XX (X.X)
Headache	X/XX (X.X)	X/XX (X.X)	X/XX (X.X)	X/XX (X.X)
Fatigue	X/XX (X.X)	X/XX (X.X)	X/XX (X.X)	X/XX (X.X)
Abdominal pain	X/XX (X.X)	X/XX (X.X)	X/XX (X.X)	X/XX (X.X)
Loss of appetite	X/XX (X.X)	X/XX (X.X)	X/XX (X.X)	X/XX (X.X)
Nausea	X/XX (X.X)	X/XX (X.X)	X/XX (X.X)	X/XX (X.X)
Vomiting	X/XX (X.X)	X/XX (X.X)	X/XX (X.X)	X/XX (X.X)
Diarrhea	X/XX (X.X)	X/XX (X.X)	X/XX (X.X)	X/XX (X.X)
Itching	X/XX (X.X)	X/XX (X.X)	X/XX (X.X)	X/XX (X.X)
Dizziness	X/XX (X.X)	X/XX (X.X)	X/XX (X.X)	X/XX (X.X)
Blurred vision	X/XX (X.X)	X/XX (X.X)	X/XX (X.X)	X/XX (X.X)

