This study will be partially blinded since it will not be known to the investigators nor the participants at the time of randomisation or drug administration whether they have been assigned to an ACT or a TACT arm. However, they will know whether they have been assigned to the AL or ASMQ based arms for the reasons outlined above and also given the differences in dosing, i.e., 6 doses for AL based arms vs 3 doses for ASMQ based arms.

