19.4.5. Risks of new partner drug combinations

No interactions between lumefantrine and amodiaquine or piperazine and mefloquine are expected. Based on the relatively safe and limited side effect profiles of both drugs, no life-threatening interactions between lumefantrine and amodiaquine are expected. Also no life-threatening interactions between piperazine and mefloquine are expected.

In addition, the preliminary results of the TRACII trial indicate that the TACTs artemether-lumefantrine+amodiaquine and DHA-piperazine+mefloquine have a good safety and tolerability profile, although both TACTs were found to induce slightly higher vomiting rates within the first hour after administration of the study drugs, compared to their matching ACTs. The safety profile of ASMQ +/- PPQ is expected to be similar to that of DHA-PPQ +/- MQ.

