#### 2.1.3. Secondary objectives and endpoints

- To compare the safety and tolerability of ACTs and TACTs within and across sites and regions, including comparisons of 'non-matching' ACTs vs TACTs (AL+Placebo versus ASMQ+PPQ, ASMQ+Placebo versus AL+AQ).
  - Incidence of adverse events and serious adverse events within the first 42 days including markers of hepatic, renal or bone marrow toxicity; cardiotoxicity, in particular QT or QTc-interval above 500 ms at timepoint H4 and H52/H64 and between these time points; change from baseline in haemoglobin at days 3, 7, 28, stratified for G6PD status/genotype; proportion of subjects requiring retreatment due to vomiting within 1 hour after administration of the study drugs; proportion of subjects that reports completing a full course of observed TACT or ACT without withdrawal of consent or exclusion from study because of drug related serious adverse event
  - Changes in the electrocardiogram (such as prolongation of the QTc-interval) in patients treated with TACT versus standard ACT
- To compare additional measures of treatment efficacy between treatment arms, including the 63-day ACPR, the post-treatment prophylactic effect of ACTs and TACTs defined as the 42-day & 63-day PCR uncorrected ACPR, gametocyte carriage, parasite clearance rates and fever clearance.

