### **3.4 Safety and tolerability of ACTs and TACTs within and across sites and regions, including comparisons of 'non-matching' ACTs vs TACTs (AL+Placebo versus ASMQ+PPQ, ASMQ+Placebo versus AL+AQ).**

Safety analyses will be based on the whole population that get administered the study drug. That is, the safety and tolerability data will be pooled from all the sites that received the same antimalarial treatment. Safety and tolerability of TACTs versus ACTs will be assessed by comparing the frequency (%) of adverse events and serious adverse events, with particular attention to abdominal pain, appetite perturbation, biochemical markers of hepatic and renal toxicity and QT interval prolongation, using the Fisher's exact test. Safety data will be presented in tabular and/or graphical format and summarized descriptively. Any clinically relevant abnormalities or values of potential clinically concern will be described. Patients will be analysed following the intention to treat analysis. All adverse event summaries will refer to treatment emergent adverse events, i.e. adverse events that newly started or increased in intensity after the study drug administration. Adverse events will be graded according to Division of AIDS table for grading the severity of ADULT AND PEDIATRIC adverse Events Version 2.0, November, 2014. The relevant DAIDS table will be appended to this document. The safety and tolerability summaries will be presented in tables 6.

The frequency and proportion of subjects that reports completing a full course of observed TACT or ACT without withdrawal of consent or exclusion from study because of drug related serious adverse events will be summarized within and across sites and regions. The 95% confidence intervals will be reported for the proportions. The proportions will be compared between matching drugs. The analyses will be summarised in table 7.

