**Table 7b. Necessity for retreatment due to vomiting or spitting study drug**

	AL+AQ	AL+Placebo	ASMQ+PPQ	ASMQ+Placebo
Number of participants	XX	XX	XX	XX
Number of total doses	XX	XX	XX	XX

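### SAP Table 6 reports vomiting per treatment while the endpoint counts subjects; the SAP should fix the subject as the unit for any vomiting test and add a row that delivers the 1-hour endpoint

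*SAP*

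**What the plan says.** Both documents list as a secondary tolerability endpoint the "proportion of subjects requiring retreatment due to vomiting within 1 hour after administration of the study drugs" (Protocol 5.2, SAP 2.1.3). The unit is the subject and the window is one hour.

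SAP 3.4 states: "Safety and tolerability of TACTs versus ACTs will be assessed by comparing the frequency (%) of adverse events and serious adverse events", and gives the method as "using the Fisher's exact test". The same paragraph says "Safety data will be presented in tabular and/or graphical format and summarized descriptively", and sends the safety and tolerability summaries to Table 6. It gives no method for repeated doses within a subject.

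Table 6 contains the row "Vomiting/number of treatments, n/N", next to a separate line for the number of subjects. Further down, its symptom block has a graded vomiting row. The table has no p-value column.

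Table 7b, titled "Necessity for retreatment due to vomiting or spitting study drug", lists participants, total doses, retreatment events and participants who vomit again after retreatment. Its vomiting row counts events at under 30 minutes. Protocol 10.2 also provides for repeat dosing after vomiting between 30 and 60 minutes.

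The regimens differ: "6 doses for AL based arms vs 3 doses for ASMQ based arms" (Protocol 9.4). SAP 2.1.3 and 3.4 plan safety and tolerability comparisons of non-matching pairs, each of which sets a six-dose regimen against a three-dose one.

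**The concern.** Early vomiting is the tolerability difference that the sponsor already has reason to expect. Protocol 19.4.5 says of the earlier trial of triple combinations that "both TACTs were found to induce slightly higher vomiting rates within the first hour after administration of the study drugs", relative to their matching ACTs.

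A row with doses as denominator raises two problems. First, a subject who vomits one dose may well be more likely to vomit another. Fisher's test on doses treats each dose as independent, so it would overstate the evidence if that correlation is positive. Second, a per-dose rate and a per-subject rate answer different questions when one regimen has twice as many doses. Within a matching pair the dose count is the same and this second problem cancels. In the non-matching comparisons it does not.

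A separate gap is that a reader looking for the stated endpoint cannot point to a table cell that will contain it.

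**Working it through.** The documents give no rate, correlation or power for the vomiting comparison, so there is no figure of the plan's own to reproduce.

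**Inputs from the documents**
- Doses per subject, k: 6 (AL arms), 3 (ASMQ arms).
- Subjects per site: 72 per ACT arm and 144 per TACT arm (SAP 2.2.1). The AL pair runs at 8 sites: 8 × 72 = 576 and 8 × 144 = 1,152. The ASMQ pair runs at 7 (not Rwanda): 7 × 72 = 504 and 7 × 144 = 1,008.
- The only early-vomiting figure is 3.4% of subjects on ASMQ (Protocol 19.4.3). It is per subject, not per dose.

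**Assumed**
- Treatments means doses, and every subject takes all of them.
- Vomiting risk is 3% per dose, with beta-binomial variation between subjects.
- Intraclass correlation (ICC) is 0.05 to 0.3.
- Fisher's test is two-sided at 0.05.

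**Step 1. Matching pairs, no true difference, Fisher's test on doses**

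The design effect is DE = 1 + (k − 1) × ICC. The approximate true size of a nominal 5% test is 2 × [1 − Φ(1.96/√DE)]. For AL at ICC 0.1, DE = 1 + 5 × 0.1 = 1.5 and 1.96/√1.5 = 1.60, giving 11.0%.

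| ICC | AL: DE | AL: formula | AL: simulated | ASMQ: DE | ASMQ: formula | ASMQ: simulated |
|---|---|---|---|---|---|---|
| 0.05 | 1.25 | 8.0% | 7% | 1.1 | 6.2% | 5–6% |
| 0.1 | 1.5 | 11.0% | 9–11% | 1.2 | 7.4% | 6–8% |
| 0.2 | 2.0 | 16.6% | 16–17% | 1.4 | 9.8% | 8–9% |
| 0.3 | 2.5 | 21.5% | 20–22% | 1.6 | 12.1% | 11–13% |

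The simulated columns give the spread over repeated runs. At ICC 0 the dose-level test rejects about 4–5% of the time. Fisher's test on subjects (vomited at least once, yes or no) stays at about 4–7% at every ICC, so it holds its level within simulation error.

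**Step 2. Non-matching pairs, same share of subjects vomiting in both arms**

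Suppose 12% of subjects vomit at least once in each arm (assumed). With independent doses, the per-dose risk is 1 − (1 − 0.12)^(1/k):
- AL: 1 − 0.88^(1/6) = 2.1%
- ASMQ: 1 − 0.88^(1/3) = 4.2%

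With correlated doses, solve 1 − B(a, b + k)/B(a, b) = 0.12 for p, where a = p(1 − ICC)/ICC and b = (1 − p)(1 − ICC)/ICC. At ICC 0.1 the per-dose rates are 2.6% and 4.6%. At ICC 0.3 they are 3.8% and 5.6%. The gap narrows as correlation rises but keeps its direction.

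The reverse also holds. An equal 2% per-dose risk with independent doses gives 1 − 0.98^6 = 11.4% of subjects vomiting under AL and 1 − 0.98^3 = 5.9% under ASMQ, and the per-dose row would hide that contrast.

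**Step 3. Which shell delivers the endpoint?**

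The endpoint needs subjects retreated for vomiting within one hour, over subjects treated.
- Table 6, per-treatment row: wrong denominator, no window, and vomiting rather than retreatment.
- Table 6, graded symptom row: neither retreatment nor the one-hour window.
- Table 7b, vomiting row: events rather than subjects, and a 30-minute window.
- Table 7b, participant line under retreatment events: counts people, but the table covers both vomiting and spitting, and the line does not separate them.
- Table 7b, participants vomiting after retreatment: concerns a second episode.

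None of these rows clearly matches.

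**The case against.** A reader might infer that the SAP plans a dose-level Fisher test of vomiting and that its p-values will therefore be too small. The documents do not go that far. The test is named for adverse event frequencies in general; SAP 3.4 also says that safety data are summarised descriptively and that patients are analysed. Tables 7a, 10 and 12 carry p-value columns and Table 6 does not. This stands: the inflation in Step 1 is conditional. It does not close the point. No row of Table 6 has a p-value column, yet SAP 3.4 says that adverse event frequencies will be compared, so the missing column does not exempt this row.

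A reader might also infer that the per-subject endpoint has been replaced. It has not. It is unchanged in Protocol 5.2 and SAP 2.1.3, and Table 7b carries participant lines. What is missing is a row that matches it.

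Three further reservations stand:
- Treatments could mean treatment courses, since Protocol 7 allows re-entry after three months and Table 7b writes doses when it means doses.
- Protocol 10.2 stops repeat dosing after more than one vomiting episode within an hour, so some repeat vomiters may leave the dosing schedule. The simulation ignores this.
- The twofold gap in Step 2 is the independent-dose extreme.

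A per-dose rate is also a legitimate description when regimens differ in dose number. The objection is to testing it as if doses were independent, or reading it as the endpoint.

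**Conclusion.** The point holds as a clarification that costs almost nothing. The unit in Table 6 differs from the unit of the endpoint, the SAP does not say how or whether that row is tested, and no shell clearly reports subjects retreated for vomiting within one hour.

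If Fisher's test were run on doses, and within-subject ICC lay between 0.05 and 0.3 at 3% vomiting per dose, the true size of a nominal 5% test would be about 7% to just over 20% in the AL pair and 5% to 12% in the ASMQ pair. With no correlation there is no inflation. Neither the ICC nor the per-dose rate comes from the documents.

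The distortion in AL-versus-ASMQ comparisons does not need a positive correlation or a formal test. It follows from six doses against three, given that treatments means doses. The mismatch between Table 7b's 30-minute row and the one-hour endpoint rests on the text alone.

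**What to change.** - Add to Table 6 or Table 7b a row for subjects with at least one retreatment due to vomiting within one hour, over subjects treated.
- State in SAP 3.4 that all between-arm vomiting tests, matching and non-matching, use that subject-level count. The Table 6 footnote already counts a subject once for QTc abnormalities and bradycardia seen at one or more time points; the same convention serves here.
- Define treatments in Table 6. Keep the per-dose rate as description, or analyse it with a logistic GEE clustered on subject.
- Align the window and unit of Table 7b with the stated endpoint and reconcile its 30-minute row with Protocol 10.2. The dosing rule itself is not at issue.

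The cost is one table row, one definition and a sentence or two in the SAP. Repeat doses and vomiting are already recorded under the protocol, so no new data are needed.

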5.2. Secondary endpoints

- For safety and tolerability: Incidence of adverse events and serious adverse events within the first 42 days including markers of hepatic, renal or bone marrow toxicity; cardiotoxicity, in particular QT or QTc-interval above 500 ms at timepoint H4 and H52/H64 and between these time points; change in haemoglobin concentration at day 3, 7, 28, stratified for G6PD status/genotype; proportion of subjects requiring retreatment due to vomiting within 1 hour after administration of the study drugs; proportion of subjects that reports completing a full course of observed TACT or ACT without withdrawal of consent or exclusion from study because of drug related serious adverse event

- For efficacy: 63-day PCR corrected and uncorrected efficacy; 42-day PCR uncorrected efficacy; parasite clearance half-life assessed by microscopy as primary parameter to determine parasite clearance; proportion of subjects with microscopically detectable *P. falciparum* parasitaemia at Day 3; fever clearance time (i.e. the time taken for the tympanic temperature to fall below 37.5 °C in patients who were febrile at inclusion); proportion of subjects with gametocytaemia during and after treatment stratified by presence of gametocytes at enrolment.
- For PK/PD interactions: Pharmacokinetic profiles and interactions (including C_{max} and AUC) of artemisinin-derivatives and partner drugs in ACT and TACT treated subjects in correlation with pharmacodynamics measures of drug efficacy; day 7 plasma levels of partner drugs in correlation with treatment efficacy and treatment arm

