15.2.2. Continuous data

These will be summarised by medians (IQR, ranges) and means (standard deviations, 95% CIs), as appropriate, and will include the parasite counts and laboratory parameters. Comparisons of continuous data will be assessed using the paired/unpaired t tests or the sign rank/Mann Whitney U tests, as appropriate.

Analyses of the parasite clearance data will be conducted to look for geographical and temporal differences.

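### SAP Table 6 gives haemoglobin change, a continuous secondary safety endpoint at three visits, one count-and-percentage cell per arm, and the SAP names no method for comparing it between arms

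*SAP*

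**What the plan says.** Both documents name the endpoint as a secondary safety measure. Protocol 5.2 lists "change in haemoglobin concentration at day 3, 7, 28, stratified for G6PD status/genotype", and SAP 2.1.3 lists "change from baseline in haemoglobin at days 3, 7, 28, stratified for G6PD status/genotype". The SAP objective it serves is to compare the safety and tolerability of ACTs and TACTs.

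In the SAP's analysis section the endpoint appears once, as the Table 6 row "Change from baseline in haemoglobin at days 3, 7, 28 (stratified for G6PD status". Each arm has a single cell holding a count, a denominator and a percentage, the same format as the vomiting and SAE rows.

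SAP 3.4, which feeds that table ("The safety and tolerability summaries will be presented in tables 6"), describes "comparing the frequency (%) of adverse events and serious adverse events" and names one test: "using the Fisher's exact test". Protocol 15.2.2, which covers laboratory parameters, says: "Comparisons of continuous data will be assessed using the paired/unpaired t tests or the sign rank/Mann Whitney U tests, as appropriate". Protocol 15.2 leaves the analysis of other endpoints to the SAP.

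**The concern.** A change in concentration has no numerator. To fill the cell, someone must choose how large a fall counts as an event, at which visit, and in which G6PD group. The plan fixes none of these, so the choice could be made after the data are seen.

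Haemoglobin may also move after treatment in every arm because of the malaria itself. What tells us about the added partner drug is the difference between a TACT and its matching ACT. A percentage per arm, on an undefined event, neither estimates that difference nor gives its precision.

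**Working it through.** **Layout.** The row label names three visits and a G6PD stratification. With at least two strata that is 3 × 2 = 6 or more summaries per arm, so 24 or more over four arms. Table 6 provides 4 cells.

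**How the SAP treats comparable data**
- Baseline haemoglobin (Table 1): mean and SD.
- QTc change (3.5): an unpaired t-test at each time point, with its own Table 8.
- Completion of the drug course (Table 7a): p-value columns for the matching pairs.
- Haemoglobin change: no named test, no summary of means, no difference and no interval.
- Haematocrit change (3.11): exploratory, with the method deferred to a separate plan.

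The documents give no SD, effect size, threshold or power for haemoglobin change, so there is no planned figure to reproduce.

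**Illustration of what is at stake.** Arm sizes follow from the sample-size section: 72 and 144 per matching pair per site. Over eight sites the artemether-lumefantrine pair has 72 × 8 = 576 and 144 × 8 = 1,152. These are planned enrolments with no losses deducted.

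Assumptions, none from the documents: haemoglobin SD 1.5 g/dL, mean fall 0.8 g/dL under ACT and 1.0 under TACT, correlation ρ between baseline and follow-up of 0.5 to 0.85, normal changes, two-sided 5% level.

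- SD of the change score: 1.5 × √(2(1 − ρ)).
- Residual SD with baseline adjustment: 1.5 × √(1 − ρ²).
- Standard error: SD × √(1/576 + 1/1,152) = SD × 0.0510.
- Power: Φ(0.2/SE − 1.96).

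At ρ = 0.5 the change-score SD is 1.50 and the SE 0.0765, so power = Φ(2.61 − 1.96) = 74%. With adjustment the SD is 1.299 and the SE 0.0663, so power = Φ(3.02 − 1.96) = 85%.

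For a dichotomy, the event probability is the chance that a normal change exceeds the cut-off. At ρ = 0.5 this is 44.7% vs 50.0% for a fall above 1 g/dL and 21.2% vs 25.2% above 2 g/dL. Fisher power was enumerated from the two binomial distributions.

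| ρ | Test on change | Baseline-adjusted | Fisher, fall > 1 g/dL | Fisher, fall > 2 g/dL |
|---|---|---|---|---|
| 0.5 | 74% | 85% | 54% | 45% |
| 0.7 | 92% | 96% | 76% | 61% |
| 0.85 | 99.8% | 99.9% | 96% | 75% |

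Against the test on change, the dichotomy loses about 4 to 20 points at 1 g/dL and 25 to 31 points at 2 g/dL. Baseline adjustment gains about 11 points at ρ = 0.5 and almost nothing at 0.85.

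**The case against.** The best defence is that this is a copied placeholder. The haemoglobin label lacks the count-and-percentage tag that the vomiting and SAE rows carry, and Protocol 15.2.2 already supplies means, medians and two-sample tests for laboratory values. In addition, SAP 3.11 plans a haematocrit analysis by study arm and G6PD status, on a day list that includes days 3, 7 and 28.

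Much of this stands. It makes the gap one of carry-over into the SAP, not the absence of any comparison in the plan. It does not close the gap. Protocol 15.2.2 offers several tests as appropriate and leaves the effect measure, visits, strata and use of baseline open. SAP 3.11 concerns haematocrit and is exploratory.

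The defence also rules out some stronger readings that a reader might infer:

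- *The SAP assigns Fisher's exact test to haemoglobin change.* The sentence in 3.4 concerns AE and SAE frequencies. The items it singles out end with "biochemical markers of hepatic and renal toxicity and QT interval prolongation, using the Fisher's exact test", and haemoglobin is not among them. The SAP names no test for this endpoint.
- *The SAP never contrasts the randomised arms on it.* SAP 1.1 analyses safety data by randomised arm, 3.4 sets TACTs against ACTs, and Table 6 places the four arms side by side. Table 6 has no contrast column for any row, including those for which a test is promised.
- *Baseline haemoglobin is ignored.* Change from baseline uses it. A change score and a baseline-adjusted model are both valid under randomisation; the choice between them is about precision.

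**Conclusion.** The point holds as a specification gap. The one row for this endpoint has a format that cannot be filled without an undefined threshold, it omits the visit and G6PD splits its own label calls for, and SAP section 3 attaches no method to it. It concerns a secondary safety endpoint and leaves the primary efficacy analysis untouched, but it should be corrected.

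The power figures only illustrate. They rest on an assumed SD, mean falls and correlation, and on full planned enrolment. A reader might infer that dichotomising always costs 25 points or more. That is not supported: the loss depends on the cut-off and is about 4 to 20 points at 1 g/dL. The gap itself does not depend on any of these numbers.

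**What to change.** Replace the Table 6 row with a separate table. For each of days 3, 7 and 28, give:

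- mean (SD) haemoglobin and mean change from baseline per arm;
- the TACT minus matching-ACT difference with 95% CI, from a linear model of haemoglobin at that visit on arm, baseline haemoglobin and site.

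Show this overall and by G6PD status where that status is known, and report the number with unknown status. Complete G6PD data should not be presumed: the Appendix 1 schedule lists no G6PD test, and Protocol 14.3 ties host genotyping to subjects with suspected abnormal pharmacokinetics or pharmacodynamics. If a proportion with a fall is also wanted, define the threshold before unblinding.

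The cost is a paragraph of SAP text, one table shell and a little analysis work. Haemoglobin is already scheduled at days 0, 3, 7 and 28 (Protocol 12.1.2), so no extra sampling is needed.
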